### **2.3.2 Concomitant medication**

Concomitant medication/non-drug treatments data will not be presented in the study report. A data listing will be produced for evaluation of protocol violations only at the blinded data review stage.

## **2.4 Analysis of skin irritation**

### **2.4.1 Primary endpoint**

#### **2.4.1.1 Primary skin irritation endpoint definition**

The primary analysis will be based on the irritation scores assessed using the dermal scale described below.

**Table 2: Skin Irritation Scoring System – Dermal Response**

Score	Skin Appearance
0	No evidence of irritation
1	Minimal erythema; barely perceptible
2	Definite erythema; readily visible; or minimal edema; or minimal popular response
3	Erythema and papules
4	Definite edema
5	Erythema, edema, and papules
6	Vesicular eruption
7	Strong reaction spreading beyond test site

Summary statistics will be presented by product group for skin irritation scores at 15-30 mins, 24 and 48 hours after patch removal. Number and percentage of subjects recording each category of skin irritation score will be presented in [Table 14.2.1.1](#). Mean, median, min and max irritation scores will be presented in [Table 14.2.1.2](#).

#### 2.4.1.2 Statistical hypothesis, model, and method of analysis

Not applicable. No formal statistical inference will be performed.

#### 2.4.2 Secondary skin irritation endpoint

##### 2.4.2.1 Secondary skin irritation endpoint definition and analysis

Secondary analysis will include effect on superficial layers of the skin as defined below.

**Table 3: Skin Irritation Scoring System – Other Effects**

Score (Numeric equivalent)	Observation
A (0)	Slight glazed appearance
B (1)	Marked glazed appearance
C (2)	Glazing with peeling and cracking
F (3)	Glazing with fissures
G (3)	Film of dried serous exudate covering all or portion of the patch site
H (3)	Small petechial erosions and/or scabs

A combined dermal response and other effect score will be derived as the sum of Dermal Response Score plus numerical equivalent for the “Other Effect” lettered score. As an example, if dermal response score=3 and superficial irritation letter =”C” then the combined score will be  $3 + 2 = 5$ . This combined score will also be summarized descriptively as the number and percent of subjects reporting/developing each category of score (Table 14.2.2.1). ”Other effect” score will be summarized descriptively as the number and percent of subjects reporting each category of score (Table 14.2.2.2).

### **2.4.3 Handling of missing values/censoring/discontinuations**

Missing data will not be replaced or imputed. Dropouts will be included in analyses up to the point of discontinuation.

## **2.5 Analysis of secondary objectives**

Not applicable.

## **2.6 Safety**

### **2.6.1.1 Adverse events and Serious Adverse Events**

All adverse events (AEs) will be summarised by primary system organ class and preferred term.

Treatment emergent adverse events (TEAEs), defined as the AEs reported after study product application, will be summarized by the number and percentage of subjects having any adverse event, an adverse event in each System Organ Class, and each individual adverse event (Table 14.3.1.1). All TEAEs will also be tabulated by severity (Table 14.3.1.2). Treatment-emergent AEs suspected of a relationship to study medication and those causing study discontinuation will be presented in a similar manner (Table 14.3.1.3). For treatment emergent-related AEs, these will also be presented by severity, if applicable (Table 14.3.1.4).

Deaths occurring during treatment (if any) will be listed (Listing 14.3.2.1) by treatment, including the date and study day of death, and the principal cause of death. Non-fatal serious adverse events and adverse events causing study treatment discontinuation will be listed (Listing 14.3.2.2).

All AEs will be listed in the Listing 16.2.7.1 and Listing 16.2.7.2.

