6.1.4 Medical History and Concomitant Medication

Medical history will be assessed as related to the inclusion/exclusion criteria by the Investigator or medically qualified designee. Details of any relevant medical or surgical history (within the last year), including allergies or drug sensitivity, will be recorded on the CRF. Any concomitant therapy taken in the 30 days prior to the Screening Visit and throughout the study will also be recorded.

6.2 Visit 2 (Day 1), Visit 3 (Day 2) and Visit 4 (Day 3)

Visit 2 may be combined with Visit 1 (Screening) but should be no more than 7 days following Visit 1.

At Visit 2 any concomitant therapy taken will be reviewed, and continued eligibility will be checked before product application (and randomisation of product application ordering). This will be reviewed again before each subsequent visit.

 GlaxoSmithKline	Document Name	207235 Clinical Protocol		
	Type	Version	Document Identifier	Effective Date
	eldo_clinical_doc	3.0; Most-Recent; Effective; CURRENT	090032d580cfa41f	07-Mar-2017 08:35:25
	Reason For Issue	Auto Issue		

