7. SAFETY ASSESSMENTS

7.1. Definitions of an Adverse Event and Serious Adverse Event

7.1.1. Adverse Events

The investigator or site staff will be responsible for detecting, documenting and reporting events that meet the definition of an AE or SAE.

Adverse Event Definition:
 
An AE is any untoward medical occurrence in a patient or clinical investigation subject, temporally associated with the use of an investigational or washout product, whether or not considered related to the investigational or washout product.
 
NOTE: An AE can therefore be any unfavorable and unintended sign (including an abnormal laboratory finding), symptom, or disease (new or exacerbated) temporally associated with the use of an investigational or washout product.

Events meeting AE definition include:
 
Any abnormal laboratory test results (if applicable) or other safety assessments,

--

 GlaxoSmithKline	Document Name	207235 Clinical Protocol		
	Type	Version	Document Identifier	Effective Date
	eldo_clinical_doc	3.0; Most-Recent; Effective; CURRENT	090032d580cfa41f	07-Mar-2017 08:35:25
	Reason For Issue	Auto Issue		

including those that worsen from baseline, and felt to be clinically significant in the medical and scientific judgment of the investigator.

Exacerbation of a chronic or intermittent pre-existing condition including either an increase in frequency and/or intensity of the condition.

New condition(s) detected or diagnosed after study product administration even though it may have been present prior to the start of the study.

Signs, symptoms, or the clinical sequelae of a suspected interaction.

Signs, symptoms, or the clinical sequelae of a suspected overdose of either study product or a concomitant medication (overdose per se will not be reported as an AE/SAE).

Events NOT meeting definition of an AE include:

Any clinically significant abnormal laboratory findings (if applicable) or other abnormal safety assessments which are associated with the underlying disease, unless judged by the investigator to be more severe than expected for the subject's condition.

The disease/disorder/ condition being studied or expected progression, signs, or symptoms of the disease/disorder being studied, unless more severe than expected for the subject's condition..

Medical or surgical procedure (e.g., endoscopy, appendectomy): the condition that leads to the procedure is an AE.

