7.2. Recording Adverse Events and Serious Adverse Events

Recording of adverse events and serious adverse events:

The investigator or site staff will be responsible for detecting, documenting and reporting events that meet the definition of an AE or SAE.

The investigator or site staff will then record all relevant information regarding an AE/SAE in the CRF.

There may be instances when copies of medical records for certain cases are requested by GSK. In this instance, all subject identifiers, with the exception of the subject number, will be blinded on the copies of the medical records prior to submission to GSK.

The investigator will attempt to establish a diagnosis of the event based on signs, symptoms, and/or other clinical information. In such cases, the diagnosis will be documented as the AE/SAE and not the individual signs/symptoms. Clinical AEs will be described by diagnosis and not by symptoms when possible (e.g., upper respiratory tract infection, seasonal allergy, etc. instead of runny nose).

AEs will be collected from the start of the product application and until **5** days following last administration of the study product.

SAEs will be collected over the same time period as stated above for AEs. However, any SAEs assessed as **related** to study participation (e.g., investigational product, protocol mandated procedures, invasive tests, or change in existing therapy) or related to a GSK concomitant medication will be recorded from the time a subject consents to participate in the study up to and including any follow-up contact.

Medical conditions reported prior to the time period for reporting AEs/SAEs should be recorded as part of the subject's medical history.

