9.3.4. Safety Analysis(es)

Adverse Events (AE) will be tabulated according to the current version of the MedDRA. Frequencies and percentages will be presented overall, for each system organ class, and for each preferred term. Summaries of treatment-emergent AEs, treatment-related AEs, AEs leading to discontinuation, and serious AEs will be

 GlaxoSmithKline	Document Name	207235 Clinical Protocol		
	Type	Version	Document Identifier	Effective Date
	eldo_clinical_doc	3.0; Most-Recent; Effective; CURRENT	090032d580cfa41f	07-Mar-2017 08:35:25
	Reason For Issue	Auto Issue		

completed. For treatment-related AEs, these will also be presented by product group/test site.

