Subject Number	Age/Sex/Race[1]	Randomization Number	Test Site/Treatment Randomised	Date of randomization (dd/mmm/yyyy)
PPD				PPD

[1] Age in years; Sex: F = Female, M = Male ; Race: A = Asian, B = Black or African American, I = American Indian or Alaska Native, H = Native Hawaiian or Other Pacific Islander, W = White, O = Multiple.

PPD

Protocol: 207235

Program Run Date:ddmmyyyy

Listing 16.2.2  
Individual Subjects Protocol Deviation  
Randomised Population

Subject Number	Age/Sex/Race[1]	Visit	DeviationSequence	Protocol Deviation
PPD				xx

[1] Age in years; Sex: F = Female, M = Male ; Race: A = Asian, B = Black or African American, I = American Indian or Alaska Native, H = Native Hawaiian or Other Pacific Islander, W = White, O = Multiple.

PPD

PPD

Protocol: 207235

Program Run Date: ddmonyyyy

Listing 16.2.7.1  
All Adverse Events  
Randomised Population  
Treatment Group: Serum X

Subject Number	Age/Sex/Race[1]	Adverse Event (Preferred Term) (System Organ Class)	Start Date /Study Day[2]	Start Time	End Date	End Time	Frequency /Intensity[3]	Related to Study Product?	Action Taken re Study Product	Outcome	Serious?	Withdrew? [4]
PPD												

[1] Age in years; Sex: F = Female, M = Male ; Race: A = Asian, B = Black or African American, I = American Indian or Alaska Native, H =Native Hawaiian or Other Pacific Islander, W = white, O = Multiple.  
 [2] Study day is the day relative to start of treatment, day 1 being the day of first treatment.  
 [3] INT = Intermittent and SGLE = Single.  
 [4] Did subject withdraw from study as a result of this adverse event?

PPD

PPD

Programming Note for Listing 16.2.7.2:

- Repeat the same layout for listing 16.2.7.2
- Population should be used 'Non randomised Subjects'
- The fourth column should be only 'Start Date'
- Add footnote 'Only SAEs are collected for non randomised subjects'
- Delete the footnote related to study day and adjust the numbers accordingly.

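### The SAP classes an AE as treatment-emergent by when it is reported, not when it starts, so a condition that began before the patch but was first reported afterwards is counted

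*SAP*

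**What the plan says.** SAP 2.6.1.1 introduces TEAEs as "defined as the AEs reported after study product application". All four AE tables in SAP 4.2 (14.3.1.1 to 14.3.1.4) are TEAE tables, and 14.3.1.1 is also a top-line output.

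The protocol uses the term without defining it. Section 9.3.4 says only: "Summaries of treatment-emergent AEs, treatment-related AEs, AEs leading to discontinuation, and serious AEs will be" completed.

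Three other protocol rules decide which events reach the SAP definition:

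- Section 7.2 sets the window: "AEs will be collected from the start of the product application and until" five days after the last administration.
- Section 7.1.1 lists among events that are AEs: "New condition(s) detected or diagnosed after study product administration even though it may have been present prior to the start of the study".
- Section 7.2 also says: "Medical conditions reported prior to the time period for reporting AEs/SAEs should be recorded as part of" the medical history.

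Protocol 6.2 allows a gap before the patch: "Visit 2 may be combined with Visit 1 (Screening) but should be no more than 7 days following Visit 1".

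Onset data are available. Listing 16.2.7.1 has columns for start date, study day and start time, with the footnote: "Study day is the day relative to start of treatment, day 1 being the day of first treatment".

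**The concern.** A treatment-emergent label should separate events that began or worsened under exposure from those already there. A rule based on reporting time does not do that. Two subjects with the same condition and the same onset before the patch can be classified differently only because one mentioned it before application and the other afterwards.

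How often AEs occur and how severe they are is the only secondary endpoint in both documents. This one sentence sets the numerator of every AE table, so events that began before exposure can raise the reported rates.

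**Working it through.** The documents give no figure for this point, so the check is mainly a comparison of texts.

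**Step 1. Follow one condition through the rules.** Suppose it starts the day before the patch is applied.

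| When it is first mentioned | Protocol rule | Result under the SAP wording | Result under an onset rule |
|---|---|---|---|
| Before application | 7.2: medical history | Not an AE | Not an AE |
| After application, newly detected | 7.1.1: AE, even if present earlier | TEAE | AE, not treatment-emergent |
| Known at the start, does not worsen | 7.1.1: not an AE | Not an AE | Not an AE |
| Known at the start, worsens after application | 7.1.1: AE | TEAE | TEAE |

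Only the second row differs. That is the scope of the problem: earlier onset, not mentioned beforehand, first reported or detected afterwards, and meeting the AE definition.

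**Step 2. Ask what the definition excludes.** Routine AE collection begins at application, so nearly every AE in a treated subject is reported after it. The exception is an SAE related to study participation, which 7.2 records from consent. One reported before application is excluded; one that starts before application and is reported afterwards is included. SAP 2.6.1.1 names all AEs and TEAEs as separate sets, but in treated subjects the two nearly coincide.

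**Step 3. See whether the visit procedures close the gap.** Screening may precede application by 0 to 7 days. The Schedule of Events places an AE assessment at Visit 2, and Protocol 3.1 and 7.4 have subjects questioned at each visit about the time since the last one. Protocol 6.2 puts the concomitant-therapy and eligibility checks before application. Neither document says whether the AE question at Visit 2 comes before or after it. The gap is narrowed but not closed.

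**Step 4. Scale per subject.**

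- All of the roughly 40 randomised subjects in the Safety population: 1/40 = 2.5 percentage points.
- Only 30 in it (the target for completers): 1/30 = 3.3 percentage points.

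The number of such subjects cannot be derived from the documents.

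**Step 5. Which tables are reached.** Tables 14.3.1.1 and 14.3.1.2 need only the TEAE flag. Tables 14.3.1.3 and 14.3.1.4 also need a suspected relationship to the product, and Protocol 7.3 has the investigator weigh timing and other causes in making that judgement.

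**The case against.** The case for leaving the text alone is fairly strong. Conditions reported earlier go to medical history, and known ones that do not worsen are not AEs. Subjects are questioned at Visit 2, and screening may fall on the same day as application. The protocol deliberately counts newly detected conditions as AEs. The error can only raise TEAE counts, not hide events. Irritation that can be scored on the Appendix 2 scales is not an AE, no inference is planned, and Listing 16.2.7.1 would show an early start date to any reader. A programmer might also take reported to mean occurring.

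Most of this stands, and it limits the size of the problem. It does not make the definition right: the second row of the table above remains, and no text ties the TEAE flag to the start date.

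A reader might infer three stronger points that the documents do not support.

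- *That every condition present before the patch becomes a TEAE.* The medical-history and non-worsening rules remove most of them.
- *That most reported background events would have begun before the patch.* Assume a constant onset rate and nothing mentioned before application. Comparing 168 h of screening gap with 68 to 76 h to Visit 5 (24 ± 2 plus 48 ± 2) gives 168/(168 + 76) = 69% to 168/(168 + 68) = 71%. But collection runs for 5 days, or 120 h, after the last administration, which gives 168/(168 + 120) = 58%. Neither figure is usable. The visit questions contradict the assumption of silence, and conditions older than screening also qualify, so the figures are not upper bounds either.
- *That the treatment-related tables are inflated by the wording alone.* They also need a separate causality judgement.

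**Conclusion.** The point holds in this limited form. The only TEAE definition in the documents rests on reporting time, and it misclassifies a condition that began before application and came to light afterwards. Each such subject shifts the TEAE rate by 2.5 to 3.3 percentage points; how many there would be is unknown. The per-subject range assumes a Safety population of between 30 and 40.

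Materiality is low. The primary endpoint and the success criterion do not depend on AEs. The reason to act is that the sentence governs every AE table and is easy to correct before unblinding.

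**What to change.** Replace the definition in SAP 2.6.1.1 with wording such as: *A TEAE is an AE whose start date and time are at or after patch application at Visit 2, or a pre-existing condition that worsens at or after that time. If a missing or partial start date or time does not show that the AE started before application, it is counted as treatment-emergent.*

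Keep the summary of all AEs by system organ class and preferred term that SAP 2.6.1.1 already promises. SAP 4.2 lists only TEAE tables, so that summary needs its own entry; the 14.3.1.1 template can be reused. Flag AEs that are not treatment-emergent in Listing 16.2.7.1, so that nothing drops out of view.

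The cost is one sentence, one derived flag and one repeated table. The flag uses the start fields already listed and the patch application time. That time is assumed to be recorded, since the 24 ± 2 h removal window cannot be checked without it. The downside is small: the default for missing start times may keep a few early events in the TEAE counts, which is the cautious direction for a safety summary.

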## **2.7 Analysis of other variables**

Not applicable.

## **2.8 Interim analysis**

No interim analysis is planned.

## **2.9 Sample size calculation**

No statistical analyses will be performed in this study. Approximately 40 subjects will be randomized to ensure at least 30 evaluable subjects complete the study. The number of subjects to be assessed (N=30 completing the study) was based on clinical considerations.

## **3 Changes to the Protocol Defined Statistical Analysis Plan**

There were no changes or deviations to the originally planned statistical analysis specified in the [protocol version 3.0 \[\(Dated: 7/Mar/2017\)\]](#).

## 4 Appendix 1:

### 4.1 List of Tables, Listings and Figures

#### 4.2 Tables

Table Number	Table Title (Population)	Template
14.1.1	Subject Disposition (All Screened Subjects)	Appendix 2
14.1.2.1	Subject Demographics and Baseline Characteristics (Safety Population)	Appendix 2
14.1.2.2	Subject Demographics and Baseline Characteristics (ITT Population)	14.1.2.1
14.2.1.1	Frequency of Dermal Response Score by Visit and Treatment (ITT Population)	Appendix 2
14.2.1.2	Average Dermal Response Score by Visit and Treatment (ITT Population)	Appendix 2
14.2.2.1	Frequency of Superficial Irritation (other effects) Score by Visit and Treatment (ITT Population)	Appendix 2
14.2.2.2	Frequency of Combined Score by Visit and Treatment (ITT Population)	Appendix 2
14.3.1.1	Treatment emergent Adverse Event (Safety Population)	Appendix 2
14.3.1.2	Treatment emergent Adverse Event by Severity (Safety Population)	Appendix 2
14.3.1.3	Treatment emergent Treatment Related Adverse Event (Safety Population)	14.3.1.1
14.3.1.4	Treatment emergent Treatment Related Adverse Event by Severity (Safety Population)	14.3.1.2

#### 4.3 Listings

Listing Number	Listing Title (Population)	Template
14.3.2.1	Listing of Deaths (Randomised population)	16.2.7.1
14.3.2.2	Listing of Serious Adverse Events leading to Discontinuation (Randomised population)	16.2.7.1
16.1.7	Randomisation information (Randomised Population)	Appendix 2
16.2.2	Individual Subjects Protocol Violation (Randomised Population)	Appendix 2
16.2.7.1	All Adverse Events (Randomised Population)	Appendix 2
16.2.7.2	All Adverse Events (Non-Randomised Subjects)	16.2.7.1

Note: If there are no data to display generate a null listing.

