Sufficient subjects will be screened such that approximately 40 subjects will be randomized to ensure approximately 30 evaluable subjects complete the entire study.

Diagnosis and Main Criteria for Inclusion

Healthy male and female volunteers aged 18 to 65 with no active dermatological conditions will be enrolled into this study.

Product Information

	Test Product 1	Test Product 2	Test Product 3	Test Product 4	Reference Product 1
Product Name	Experimental Daily Defense Serum A	Experimental Daily Defense Serum C	Experimental Daily Defense Serum G	Experimental Daily Defense Serum N	Saline Solution Sodium Chloride (NaCl; 0.9% _{aq})
Product Formulation Code (MFC)	CCI [REDACTED]	CCI [REDACTED]	CCI [REDACTED]	CCI [REDACTED]	N/A Site to Supply
Dose	0.02ml/cm ²				
Route of Administration	Topical application via semi occlusive patch				

 GlaxoSmithKline	Document Name	207235 Clinical Protocol		
	Type	Version	Document Identifier	Effective Date
	eldo_clinical_doc	3.0; Most-Recent; Effective; CURRENT	090032d580cfa41f	07-Mar-2017 08:35:25
	Reason For Issue	Auto Issue		

Statistical Methods

The primary evaluation will be the irritation scores after patch removal for each of the four test formulations.

The study will be considered a success if no irritation is observed which is attributable to the test product at any time point, or if any observed irritation for the test product is not clinically differentiable from the saline solution

~~The primary outcome for success is that there will be no evidence of irritation observed in the test products at any time point attributable to the product.~~

No formal statistical inference will be performed. Summary statistics will be presented by product group for skin irritation scores at 15-30 mins, 24 and 48 hours after patch removal. These will include mean irritation scores (if any subjects have reported irritation) and the number and percentage of subjects recording each category of skin irritation scores.

Adverse Events (AE) will be tabulated by the sponsor according to the current version of the Medical Dictionary for Regulatory Activities (MedDRA). Frequencies and percentages will be presented overall, for each system organ class, and for each preferred term. Summaries of treatment-emergent AEs, treatment-related AEs, AEs leading to discontinuation, and serious AEs will be completed. For treatment-related AEs, these will also be presented by product group/test site.

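### Listing 14.3.2.2 has two incompatible definitions in the SAP, and two AE summaries promised by the protocol have no matching table title

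*SAP*

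**What the plan says.** **Protocol.** The synopsis (Statistical Methods) and section 9.3.4 commit to four kinds of AE summary: "Summaries of treatment-emergent AEs, treatment-related AEs, AEs leading to discontinuation, and serious AEs will be completed".

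**SAP text, 2.6.1.1.** On the listing: "Non-fatal serious adverse events and adverse events causing study treatment discontinuation will be listed (Listing 14.3.2.2". On the tables: "Treatment-emergent AEs suspected of a relationship to study medication and those causing study discontinuation will be presented in a similar manner (Table 14.3.1.3". On deaths: "Deaths occurring during treatment (if any) will be listed", in Listing 14.3.2.1. The same section sends every AE to Listings 16.2.7.1 and 16.2.7.2.

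**SAP output list, 4.2 and 4.3.** Listing 14.3.2.2 is "Listing of Serious Adverse Events leading to Discontinuation (Randomised population". Table 14.3.1.3 is "Treatment emergent Treatment Related Adverse Event (Safety Population". The safety tables are TEAEs (treatment-emergent AEs) and related TEAEs, each repeated by severity. The title of Listing 14.3.2.1 covers deaths in the randomised population and sets no time limit. A note under 4.3 asks for a null listing where there is nothing to show.

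**SAP section 3.** "There were no changes or deviations to the originally planned statistical analysis specified in the" protocol version 3.0.

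**The concern.** The text gives Listing 14.3.2.2 a union of two groups of events; the title gives it their intersection. No template settles which applies, because the listing borrows the layout of 16.2.7.1, which carries no selection rule.

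A programmer who works from the output list would select only events that are both serious and led to discontinuation. Exposure is one patch, and after its removal only observation visits remain, so an SAE need not end participation. An SAE in a subject who completes Visit 5, or a non-serious AE that made a subject leave, would then be absent from the listing meant to show it. With the null-listing instruction, the report could carry an empty 14.3.2.2, which a reader could take to mean that neither kind of event occurred.

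General safety is the study's only secondary objective. A statement of no change from protocol should hold for the summaries that serve it.

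**Working it through.** No sample size, rate or test is involved, so the check sets the passages side by side.

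**Step 1. What each definition of Listing 14.3.2.2 selects.** Sort non-fatal AEs by seriousness and by whether they led to discontinuation, which gives 2 × 2 = 4 cells.

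| Non-fatal AE | SAP 2.6.1.1 text | SAP 4.3 title | Listing 16.2.7.1 |
|---|---|---|---|
| Serious, discontinued | in | in | in |
| Serious, stayed | in | out | in |
| Non-serious, discontinued | in | out | in |
| Non-serious, stayed | out | out | in |
| Cells covered | 3 of 4 | 1 of 4 | 4 of 4 |

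The title loses 3 − 1 = 2 cells that the text includes.

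**Step 2. Protocol summaries against SAP tables.**

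| Promised in protocol 9.3.4 and synopsis | Assigned in SAP 2.6.1.1 text | Matching title in SAP 4.2 |
|---|---|---|
| Treatment-emergent | 14.3.1.1, 14.3.1.2 | yes |
| Treatment-related | 14.3.1.3, 14.3.1.4 | yes |
| Leading to discontinuation | 14.3.1.3 | no; title limited to related events |
| Serious | none | none |

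By title, 2 of 4 summaries are provided. By text it is 3 of 4. Only the SAE summary is missing from both. If Table 14.3.1.3 follows its title, a discontinuation judged unrelated is left out, and a related one is included but not identified as a discontinuation.

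**Step 3. Where the omitted events remain visible.** Listing 16.2.7.1 shows every AE in randomised subjects, and its template has Serious, Outcome and Withdrew columns. If treatment-emergent, the events are counted in Tables 14.3.1.1 and 14.3.1.2. Table 14.1.1 counts non-completers whose reason was an AE, though not which event.

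**Step 4. Deaths.** The text limits the listing to the treatment period, a term the SAP does not define; the title sets no limit. Protocol 7.2 collects SAEs from application until 5 days after last administration, and related SAEs from consent through any follow-up contact. If treatment meant only patch wear (an assumption), a later death would fit neither text description, since 14.3.2.2 is there confined to non-fatal SAEs. It would still fit the title of 14.3.2.1 and be listed in 16.2.7.1.

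**The case against.** The strongest reply is that this is a clerical slip in the output list and that SAP 2.6.1.1 states the intent. There is support for that: SAP 4.2 also exchanges the titles of Tables 14.2.2.1 and 14.2.2.2, and there the body text and the templates agree against the list. The study is also small (about 40 randomised), healthy volunteers wear one patch, and Listing 16.2.7.1 is among the top-line outputs, so a careful reader would find the events.

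Much of this stands. A reader might infer that these events are dropped from the safety outputs altogether. They are not, as Step 3 shows. A reader might also infer that a non-serious AE causing withdrawal appears in no discontinuation output. Table 14.1.1 counts it and Listing 16.2.7.1 flags it. Nor do the documents show that deaths after patch removal go unlisted: that needs the text to govern for deaths while the title governs for SAEs, and it needs an assumed meaning for the treatment period. The protocol promises no separate deaths summary.

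The reply does not remove the contradiction. A probable slip in the list used for programming still has to be corrected, because following the list produces the wrong selection. It also does not supply the SAE table, which neither text nor list contains.

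**Conclusion.** The point holds as an internal contradiction plus an undeclared departure from protocol. If programmed to its title, Listing 14.3.2.2 covers 1 of the 4 types of non-fatal AE instead of the 3 the text specifies, and could print as null although an SAE or an AE-driven withdrawal exists. The SAP has no SAE table, and its discontinuation table exists in the text but not in the title it points to. The statement of no change in SAP section 3 is therefore inaccurate.

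What is at risk is the dedicated listing and two separate summaries; the events themselves stay in the report. The effect on the listing depends on the title being followed, which the documents leave open. They give no event rates, so how often this would matter cannot be sized. The deaths wording is the weakest part: an undefined phrase that disagrees with its own listing title. The corrections should be made before programming.

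**What to change.** 1. Retitle Listing 14.3.2.2 to match SAP 2.6.1.1 and select Serious = Yes OR Withdrew = Yes, stating whether fatal events are excluded as the text implies. SAP 2.6.1.1 speaks of stopping study treatment in one place and leaving the study in another, while the Withdrew column records leaving the study; state which is meant.
2. Add two tables on the 14.3.1.1 template, one for serious TEAEs and one for TEAEs leading to discontinuation, and correct the reference to Table 14.3.1.3. Otherwise declare the omission in section 3.
3. In the deaths sentence, replace the undefined time limit with wording that fits the unrestricted title of Listing 14.3.2.1 and the collection rules in protocol 7.2. One window starting at consent for all deaths would not fit, because before application only related SAEs are collected.

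The cost is SAP wording and two tables from an existing template. The Serious and Withdrew fields are in the listing template; the case report form itself is not in the documents. The downside is probably two near-empty tables.
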